9.6 Off Study/Off Treatment Criteria

Subject choice: Subjects may withdraw from the study at any time. The risks of withdrawing will be discussed, as will alternative treatment options. The subject will be informed that his/her condition poses a high mortality rate. The risks of not receiving further therapy include a high mortality rate with supportive care only. Those subjects who choose to withdraw will be strongly encouraged to continue to have blood counts monitored until initiation of alternative SAA therapy or through the 6 month off study medication to assess for late occurring adverse events.

Principal investigator decision: Should any of the following events occur, study drug administration will be discontinued. The subject will be followed until resolution of the event and laboratory values monitored through 6 months or until initiation of alternative SAA therapy:

- Intolerance of eltrombopag not resolved by dose reduction
- Thrombosis/embolism (DVT, PE, stroke or TIA, myocardial infarction) other than central line thrombosis
- Persistent hepatotoxicity as defined in section 5.3
- Infusion-related h-ATG reactions refractory to all appropriate supportive measures
- Life threatening acute hypersensitivity reactions
- Pregnancy or unwillingness to refrain from pregnancy
- Initiation of additional immunosuppressive therapy other than steroids or cyclosporine (if beyond 6 months then mycophenolate mofetil can also be administered per PI discretion in patients who cannot tolerate cyclosporine and who require immunosuppression) or if beyond 2 years, sirolimus per protocol 17-H-0019
- Evidence of a clonal disorder identified in subjects with super severe baseline neutropenia (ANC < 200/ μ L) who were not initially excluded because cytogenetics was not available or pending.

There are risks to pregnancy for patients with aplastic anemia or a history of aplastic anemia, and it is generally advised against, regardless of participation in a research trial. For this protocol, if pregnancy occurs when a patient is not actively receiving medical drugs, it will not be cause for withdrawal from study.

Completion of protocol participation: After 5 years, protocol participation will be deemed complete. Once off study, subjects will be referred back to the referring physician or consented to the Hematology Branch evaluation and treatment protocol (94-H-0010) or evaluated for eligibility for another Branch protocol, depending on the wishes of the subject and availability of appropriate additional clinical trials at the NIH.

Death: Death of Subject

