5.3 Eltrombopag

Subjects will initiate eltrombopag at a starting daily dose as detailed in Table 3, according to age and ethnicity. Subjects between 12 and 17 years of age will receive the adult dose of 150 mg. Those between 6 and 11 will start at 75 mg, and children between 2 and 5 years of age will be started at 2.5 mg/kg (Table 3). To adjust for the higher expected exposure in children of East Asian and South East Asian ancestry, the starting dose for East Asian and South East Asian subjects between 12 and 17 years of age will be 75 mg once daily. For East Asian and South East Asian subjects between 6 and 11 years of age, the starting dose will be 37.5 mg once daily, and for children between 2 and 5, the starting dose will be 1.25 mg/kg (Table 3). Eltrombopag will be administered orally as tablets or an oral suspension from sachet of eltrombopag powder. Each 25 mg Pfos sachet contains eltrombopag olamine equivalent to 25 mg of eltrombopag free acid. If a child's dose is based on body weight and needs a dose of 28 mg, then dose only single sachet that provides 25 mg dose. However, if the child needs a dose of 29 mg or greater, then the suggestion is to start using the second sachet. This is mainly suggested to prevent the wastage of medicine by opening a second sachet to meet the additional 1-3 mg dose. Dosing 25 mg where a patient needs 28 mg should not have a significant impact on PD response. If an adult receives the oral suspension administration of eltrombopag, the required number of sachets will be used to administer the below adult doses.

Table 3. Dosing according to age and ethnicity

Age groups	Daily dose
Non-Asian	
12-85	150 mg
6-11	75 mg

Age groups	Daily dose
2-5	2.5 mg/kg
East Asian, South East Asian	
12-85	75 mg
6-11	37.5 mg
2-5	1.25 mg/kg

Eltrombopag may be taken on an empty stomach (1 hour before or 2 hours after a meal) or with food containing little (<50 mg) or preferably no calcium or dairy products. Allow at least a 4-hour interval between eltrombopag and other medications or products containing polyvalent cations (e.g. calcium, magnesium, aluminum, zinc, selenium or iron) such as antacids, dairy products, and mineral supplements to avoid significant (70-75%) reduction in eltrombopag absorption due to chelation.

Dose delay or dosing interruptions:

Cohort 1:

Eltrombopag dose may be interrupted when clinically indicated at the discretion of the investigator. Interruptions will be recorded in the medical record.

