Cohort 2, 3, Extension Cohort and Exploratory Laboratory Cohort:

The first dose of eltrombopag may be delayed if it is clinically indicated or other unforeseen events affect the start of eltrombopag (for example weather related) at the discretion of the investigator.

Eltrombopag dose may be interrupted when clinically indicated at the discretion of the investigator (for example if the patient is in the intensive care unit and unable to take PO medications). For subjects on cohort 2, if eltrombopag dosing is delayed or interrupted for more than 1 week (7 days) and the interruption is not the result of a severe adverse event related to eltrombopag, then the subject will receive additional eltrombopag in order to receive a total of 10 weeks as originally planned for cohort 2.

Medication dosing errors, dose delays or dosing interruptions:

Interruptions such as delays in request for medication refills or medication errors by subjects will be recorded in the medical record.

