5.4 Dose Adjustments of Eltrombopag

The daily dose of eltrombopag will be decreased according to the following rules:

Platelet Count	Dose Adjustment or Response
>200,000/ μ L (untransfused) at any time on study	Decrease dosage by 25mg every 2 weeks to lowest dosage that maintains platelet count \geq 50,000/ μ L. In children under 12, the dose will be decreased by 12.5 mg.
>400,000/ μ L (untransfused) at any time on study	Discontinue eltrombopag for one week, if platelets fall to <200,000/ μ L; restart at dosage decreased by 25 mg/day (or 12.5 mg in children under 12).

5.5 Dose Delays, Modifications or Discontinuation of Eltrombopag for Non-Hematologic Side Effects

5.5.1 Infection: Subjects who experience an infection requiring intravenous antibiotics will not have eltrombopag discontinued. If the subject experiences infection severe enough to require vasopressors or intubation, the drug will be withheld until the subject is stable.

5.5.2 Liver function abnormalities:

Cohorts 1 and 2:

In the event of an increase in the ALT level to > 6 times the ULN, subjects will return to clinic or have blood tests drawn by their home physician every 3-4 days. If the ALT remains > 6 times the ULN on a second blood test, eltrombopag will be discontinued until ALT is < 5 times the ULN. Eltrombopag will be restarted at a dose level 25 mg/day lower than the prior dose. If liver test abnormalities return to an ALT of > 6 times ULN on this reduced dose, the eltrombopag dose will be reduced by 25 mg/day until there is reduction of ULN to < 5 ULN.

Cohort 3 Extension Cohort and Exploratory Laboratory Cohort:

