Transient hepatotoxicity is an expected and common side effect of h-ATG that occurs during the first 14 days following the start of h-ATG administration. In the event of an increase in the ALT level to > 6 times the ULN during Days 1 – Days 14, eltrombopag will be held until ALT is < 5 times the ULN and then resumed at the same dose. If the ALT rises to > 6 times ULN after resuming eltrombopag (and is not attributable to other inciting factors such as serum sickness, sepsis, or azole antifungal agents) then the ALT will be monitored at least every 3-4 days. If the ALT remains > 6 times the ULN on repeat blood tests, eltrombopag will be stopped until the ALT is < 5 times the ULN. Then eltrombopag will be restarted at a dose level that is 25 mg/day lower than the prior dose. If liver test abnormalities return to an ALT of > 6 times ULN on this reduced dose, the eltrombopag dose will be reduced by 25 mg/day until there is reduction of ULN to < 5 ULN.

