If the potential benefit for reinitiating treatment with PROMACTA is considered to outweigh the risk for hepatotoxicity, then consider cautiously reintroducing PROMACTA and measure serum liver tests weekly during the dose adjustment phase. Hepatotoxicity may reoccur if PROMACTA is reinitiated. If liver test abnormalities persist, worsen, or recur, then permanently discontinue PROMACTA.

Isolated cases of severe liver injury were identified in clinical trials. The elevation of liver laboratory values occurred approximately three months after initiation of PROMACTA. In all cases, the event resolved following PROMACTA discontinuation.

Thrombotic/Thromboembolic Complications

Thrombotic/thromboembolic complications may result from increases in platelet counts with PROMACTA. Reported thrombotic/thromboembolic complications included both venous and arterial events and were observed at low and at normal platelet counts.

Consider the potential for an increased risk of thromboembolism when administering PROMACTA to patients with known risk factors for thromboembolism (e.g., Factor V Leiden, ATIII deficiency, antiphospholipid syndrome, chronic liver disease). To minimize the risk for thrombotic/thromboembolic complications, do not use PROMACTA in an attempt to normalize platelet counts. Follow the dose adjustment guidelines to achieve and maintain target platelet counts.

In two controlled clinical trials in patients with chronic hepatitis C and thrombocytopenia, 3% (31/955) treated with PROMACTA experienced a thrombotic event compared with 1% (5/484) on placebo. The majority of events were of the portal venous system (1% in patients treated with PROMACTA versus less than 1% for placebo).

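### The hepatic stop criterion in 9.6 points to a definition that does not exist, and the 25 mg/day reduction rule in 5.5.2 states no step interval, lowest dose or child-sized step

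*Combined protocol and SAP*

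**What the plan says.** Section 9.6 lists events after which study drug is discontinued. One of them is "Persistent hepatotoxicity as defined in section 5.3".

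Section 5.3 sets starting doses by age and ancestry, explains how to take the drug, and covers delays and interruptions. On stopping it says only: "Eltrombopag dose may be interrupted when clinically indicated at the discretion of the investigator". It names no liver test.

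The liver rules are in 5.5.2, to which section 5.10 refers correctly. They come in two versions.

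- **Cohorts 1 and 2.** If a second test confirms ALT above 6 times ULN, "eltrombopag will be discontinued until ALT is < 5 times the ULN". Drug then restarts 25 mg/day lower.
- **Cohort 3 and later.** For a rise in the first 14 days, "eltrombopag will be held until ALT is < 5 times the ULN and then resumed at the same dose". A later confirmed rise with no other explanation brings a second stop and a restart 25 mg/day lower.

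Both versions end alike. If ALT again exceeds that limit, the instruction reads: "on this reduced dose, the eltrombopag dose will be reduced by 25 mg/day until there is reduction of ULN to < 5 ULN".

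For platelet-driven reductions, 5.4 uses a smaller step: "In children under 12, the dose will be decreased by 12.5 mg". Section 5.5.2 does not repeat it. Among East and South East Asian subjects, 5.3 states that "for children between 2 and 5, the starting dose will be 1.25 mg/kg".

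The prescribing information reproduced in 11.4.3 says: "If liver test abnormalities persist, worsen, or recur, then permanently discontinue PROMACTA".

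**The concern.** The criterion in 9.6 is the only liver-specific rule in the plan that ends eltrombopag treatment. If its reference leads nowhere, two investigators with the same patient can reach different decisions and neither can be checked against the protocol.

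The recurrence sentence in 5.5.2 makes this matter more. Earlier elevations interrupt drug until ALT is below 5 times ULN. Recurrence on a reduced dose prescribes only a cut, so without a clinician's intervention the subject stays on drug while ALT is above 6 times ULN. The text does not say how long each step lasts or when the sequence ends if ALT does not fall.

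A fixed 25 mg step is also large against a starting dose of 15 to 37.5 mg, so in some young children the rule gives a dose that cannot be prescribed.

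**Working it through.** No statistical figure is involved. The check consists of tracing the reference, comparing the action at each elevation, and running the dose step through Table 3.

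**1. The reference.** 9.6 points to 5.3, which has no liver text. The liver rules in 5.5.2 never use the term. Correcting the number alone would therefore still leave the criterion undefined.

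**2. Action at each ALT above 6 times ULN.**

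| Elevation | Cohorts 1 and 2 | Cohort 3 and later |
|---|---|---|
| Days 1-14 | no separate rule | hold, resume at same dose |
| Confirmed, before any reduction | stop, restart 25 mg/day lower | stop, restart 25 mg/day lower (after resumption) |
| Return on the reduced dose | cut by 25 mg/day | cut by 25 mg/day |

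The last row gives no hold, interval, lowest dose or permanent stop.

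**3. Dose ladder.** Dose after k reductions = starting dose - 25k, where k = 1 is the first restart. Starting doses are from 5.3. The weight limit (more than 12 kg) is from 4.1; 20 kg is an assumed upper weight for ages 2-5.

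| Group | Start (mg) | First restart | Next | Then |
|---|---|---|---|---|
| 12 and over, non-Asian | 150 | 125 | 100 | 75, 50, 25, 0 |
| 12 and over, East/South East Asian | 75 | 50 | 25 | 0 |
| 6-11, non-Asian | 75 | 50 | 25 | 0 |
| 6-11, East/South East Asian | 37.5 | 12.5 | -12.5 | |
| 2-5, non-Asian, 12 kg | 2.5 x 12 = 30 | 5 | -20 | |
| 2-5, non-Asian, 20 kg | 2.5 x 20 = 50 | 25 | 0 | |
| 2-5, East/South East Asian, 12 kg | 1.25 x 12 = 15 | -10 | | |
| 2-5, East/South East Asian, 20 kg | 1.25 x 20 = 25 | 0 | | |

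The 20 kg assumption is also the break point. For non-Asian children the second reduction is positive only if 2.5w - 50 > 0, that is w > 20 kg. For East/South East Asian children the first restart is positive only if 1.25w - 25 > 0, again w > 20 kg.

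With a 12.5 mg step under age 12 the ladders become:

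- 75, 62.5, 50
- 37.5, 25, 12.5
- 30-50, 17.5-37.5, 5-25
- 15-25, 2.5-12.5, then no lower dose (-10 to 0)

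**4. Time on drug during recurrence.** It cannot be derived, because no step interval is stated. If cuts followed the ALT tests that 5.5.2 sets every 3-4 days (an assumption), going from 100 mg to 0 takes four more cuts: 4 x 3 = 12 to 4 x 4 = 16 days after the first.

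**5. Reach.** Section 2.9.4 reports 178 of 182 accrued. The 182 counts 33 places in cohort 2, of which 31 were used (2.9.1). Places that could be filled: 31 + 31 + 31 + 87 = 180. Left to enrol: 180 - 178 = 2, plus 25 laboratory subjects = 27. The same section gives 86 in the extension cohort against a ceiling of 87, which leaves 1 + 25 = 26.

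Section 11.1 expects 20% under 18 and 6% Asian. Assume ages 2-17 are uniform and ancestry is independent of age.

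- Ages 2-5: 0.20 x 4/16 = 5%.
- Asian ages 6-11: 0.20 x 6/16 x 0.06 = 0.45%.
- Together 5.45%, or 1.4 of 26 to 1.5 of 27.
- Impossible first restart (Asian ages 2-5): 0.05 x 0.06 = 0.3%, or 0.08 of 27.

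Whatever the age split, subjects under 18 are 0.20 x 27 = 5.4. All these counts are before any ALT event.

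**The case against.** **Backstops exist.** ALT above 6 times ULN triggers testing every 3-4 days. Section 5.3 allows interruption at discretion, and 9.6 also stops drug for intolerance that lowering the dose has not settled, which naturally covers ALT that will not fall. In adults the ladder runs to zero. This stands, and it limits the harm. But neither stopping provision has an ALT level, a duration or a number of reductions, and 9.6 lists hepatotoxicity as a separate criterion that still has no content.

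**Reducing rather than stopping is defensible.** Cyclosporine and h-ATG also raise transaminases, and 11.4.2 says rises on cyclosporine often settle with continued dosing. In cohort 3 and later, recurrence on the reduced dose can be the third elevation, but the first is then an expected h-ATG effect. This also stands. Whether to hold at recurrence is a clinical choice.

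**Stronger readings a reader might infer.**

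- *The plan breaches the label.* The label sentence closes a scheme that starts at 3 times ULN. The trial openly works at 6 times ULN, and 11.4.3 reproduces the text as risk information, not as a trial rule. The contrast shows a gap; it does not show a violation.
- *Children may be overdosed.* A zero or negative dose means no drug. Most of the paediatric count is non-Asian children aged 2-5, whose first restart is positive and whose next step ends treatment.
- *Four extension places plus 25 leaves 29 to enrol.* This counts two cohort 2 places that were never used.
- *The expected number of recurrences can be estimated.* The 12% with increased transaminases in 11.4.3 is any increase, not a return above 6 times ULN. Historical relapse rates do not tell how many subjects will restart eltrombopag, since cohort 1 and 2 relapses may be treated with cyclosporine alone (5.7).

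**Conclusion.** The point holds as a defect of specification. The liver-specific stop criterion in 9.6 has a wrong reference and no definition anywhere. The recurrence rule in 5.5.2 lacks a step interval, a lowest dose and any end point other than ALT below 5 times ULN. The unscaled step gives zero or negative doses in East/South East Asian children aged 6-11 and in children aged 2-5 up to 20 kg.

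The documents do not show that subjects would be kept on drug indefinitely at high ALT, or that a permanent stop at first recurrence is required.

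Reach is small: about 26-27 subjects left to enrol when 2.9.4 was written, of whom perhaps 1.4-1.5 fall in an affected paediatric group under the stated age and ancestry assumptions. Subjects who relapse and restart eltrombopag under 5.7 are added; their number is not stated. Sample size, endpoints and analysis are unaffected. Severity: minor to moderate.

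**What to change.** 1. **Reference and definition.** In 9.6, refer to 5.5.2. In 5.5.2, define persistent hepatotoxicity as ALT above 6 times ULN, not explained by another cause such as serum sickness, sepsis or an azole, that despite dose reduction recurs or does not fall below 5 times ULN within a period chosen by the sponsor, or for which no lower dose is available. Keeping the other-cause exemption avoids ending eltrombopag for an unrelated rise.
2. **Step size and floor.** In both paragraphs of 5.5.2, make every reduction, including the first restart, 25 mg/day, or 12.5 mg/day under age 12 as in 5.4. Discontinue when no lower dose exists.
3. **Optional, at the sponsor's clinical judgement.** On recurrence at the reduced dose, hold until ALT is below 5 times ULN before restarting one step lower, as at the earlier elevations. If this is adopted, the definition in item 1 should say whether recurrence is counted before or after that restart.

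The cost is one short clarifying amendment. The downside is that a few subjects with recurrent ALT elevation may lose some eltrombopag exposure.

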At the 6-month landmark visit, responders will have the CsA dose reduced to 2.0mg/kg/day administered orally at a fixed dose through the 24 month timepoint. Previous anecdotal experience suggested that a gradual taper of CsA may avoid relapse, but when we adopted this strategy prospectively in our clinical trials (03-H-0193 and 06-H-0034) the rate of relapse was unchanged (Scheinberg, Rios, et al. AJH 2014⁶⁷). However, time to relapse was delayed by 1 year with the longer course of CsA and may be dose-dependent. The CsA dose at the time of relapse during the taper phase was at a median of 1.32 (range: 0.52-4.18) mg/kg/day and a mean of 1.8 mg/kg/day. This suggests that a CsA dose level above these levels might preclude relapse and improve tolerability of chronic maintenance. For remaining subjects due for the 6 month timepoint on cohort 2 we will prolong administration of cyclosporine beyond 6 months. CsA will continue to be administered from Day 1 to 6 months, but from 6 months to 2 years CsA will be administered at a lower fixed daily dose (2 mg/kg/day) in an attempt to improve relapse, a secondary endpoint, among responders in the study.

Medication dosing errors, dose delays or dosing interruptions:

Interruptions such as delays in request for medication refills or medication errors by subjects will be recorded in the medical record.

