6.4 Long Term Follow Up (12 months to 5 years)

After the 6 month visit, subjects must be evaluated at the Clinical Center at 12 months (+/- 30 days) and then yearly thereafter to 5 years (+/- 90 days for Years 1 & 2; +/- 1 Year for Years 3 & 4). Subjects will be seen by their home physician as clinically indicated and the Hematology Branch investigators and home physicians will remain in communication. Home physicians will monitor blood counts and other clinical parameters as clinically indicated. The following tests will be performed at each Clinical Center visit. At the clinical investigator's discretion, participants may be evaluated more frequently if medically indicated based on disease status. If a subject is unable to present to CC for landmark Year 3 or 4 follow up due to circumstances beyond their control and their peripheral blood counts are available and stable compared to last visit at CC, the subject may remain on the study and follow up as soon as able but no longer than 1 year from the missed visit.

- Complete blood counts with differential
- Acute care, Mineral, Hepatic and Other panel
- Reticulocyte count
- Bone marrow aspiration and core biopsy, to be stained for standard morphologic analysis and quantitation of cellularity with hematoxylin and eosin, and special stains to assess reticulin and collagen, primitive stem and progenitor cells via CD34 immunohistochemistry, and other lineage-specific or special stains as indicated to classify any abnormalities.
- Bone marrow chromosomal analysis via standard cytogenetic techniques
- Flow cytometry of the peripheral blood to quantitate GPI-negative cells
- Lymphocyte peripheral blood phenotyping
- HRQL survey administration (Surveys will not be required for the Extension and Exploratory Laboratory Cohorts.)

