9.2 Statistical Methods

For each cohort, the planned analyses will include descriptive statistics on the proportions of responses (% subjects with partial or complete response), cumulative incidence of response with death considered to be a competing risk and the time to complete response. The response probabilities, including complete response probability and partial response probability, will be estimated using the sample proportions, and their inferences, including confidence intervals and hypotheses testing, will be evaluated using Binomial distributions. Survival analysis will include methods based on Kaplan-Meier estimates and Cox regression. Although we have a small sample size, if it is appropriate, we will consider additional analyses for the primary and secondary endpoints using the analysis of variance, multiple regression and logistic regression models. Graphical tools will be used to display the appropriate estimates (i.e. estimated proportions and Kaplan-Meier curves) and their corresponding 95% confidence intervals.

Results for each cohort will be compared separately to the historical data from the large numbers of patients treated at the NIH previously with either a single or repeat course of immunosuppression from prior NHLBI studies: the h-ATG/CsA protocol (90-H-0146); the h-ATG/CsA vs. Cytoxin/CsA protocol (97-H-0117); the h-ATG/CsA/MMF protocol (00-H-0032); the h-ATG/CsA/Rapamune protocol (03-H-0193); the r-ATG vs. alemtuzumab protocol (03-H-0249); and h-ATG/CsA vs. r-ATG/CsA protocol (06-H-0034). More specifically, results from the current trial will be compared to our large historical experience with a horse ATG based regimen in nearly 400 patients (from the aforementioned studies) of a hematologic response rate of 60-70%, a complete response rate of 10-15%, a relapse rate of 30-40%, a clonal evolution rate (any clonal abnormality) of 15-20%, and a high risk evolution rate (to monosomy 7, high risk MDS, leukemia, or complex cytogenetics) of 10-15%.

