9.4 Secondary Endpoints

Secondary endpoints will also be evaluated for the study to include: (a) hematological response at 3 and 12 months and yearly thereafter; (b) relapse (c) clonal evolution to PNH, clonal chromosomal population in bone marrow, myelodysplasia by morphology, or acute leukemia; (d) survival; (e) health-related quality of life; (f) hematological response of relapse subjects that re-start treatment; and (g) affects of a 2.0mg/kg/day CsA dose starting month 6 for 18 months until month 24 on the rate of relapse of subjects deemed responders at month 6.

Subjects will be followed up to 60 months so that long-term disease-free and overall survival can be estimated. Response and toxicity comparisons will also be made with the results obtained from prior NHLBI studies: the h-ATG/CsA protocol (90-H-0146); the h-ATG/CsA vs. Cytoxan/CsA protocol (97-H-0117); the h-ATG/CsA/MMF protocol (00-H-0032); the h-ATG/CsA/Rapamune protocol (03-H-0193); the 3-arm randomized study (06-H-0034) and the r-ATG vs. alemtuzumab (03-H-0249) trials.

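### Section 9.6 gives no follow-up to subjects who start other immunosuppression, in conflict with the 60-month survival and clonal-evolution follow-up in 9.4 and 6.4

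*Combined protocol and SAP*

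**What the plan says.** - **Section 9.6, trigger.** The list of events left to the principal investigator's decision includes "Initiation of additional immunosuppressive therapy other than steroids or cyclosporine". Mycophenolate is excepted beyond 6 months for subjects who cannot tolerate cyclosporine (CsA), and a second exception reads "or if beyond 2 years, sirolimus per protocol 17-H-0019".
- **Section 9.6, consequence.** The lead-in to the list says "Should any of the following events occur, study drug administration will be discontinued". It continues: "The subject will be followed until resolution of the event and laboratory values monitored through 6 months or until initiation of alternative SAA therapy".
- **Section 9.4.** "Subjects will be followed up to 60 months so that long-term disease-free and overall survival can be estimated". Clonal evolution and survival are both secondary endpoints.
- **Section 6.4.** After the 6-month visit, "subjects must be evaluated at the Clinical Center at 12 months" and then yearly to 5 years, with marrow cytogenetics at each Clinical Center visit.
- **Section 9.2.** Survival is analyzed by Kaplan-Meier and Cox regression, with no rule for subjects who meet a 9.6 criterion. Each cohort is compared separately with "patients treated at the NIH previously with either a single or repeat course of immunosuppression". The historical rates given are for response, complete response, relapse, any clonal evolution (15-20%) and high-risk evolution (10-15%).

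**The concern.** For most events on the list, monitoring until alternative therapy starts leaves some period of observation. For this event, the start of alternative therapy is the event, so the rule leaves none. It mentions neither vital status nor cytogenetics.

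The subjects concerned have a poor prognosis. Relapsers re-treated with eltrombopag or CsA stay on protocol (5.7), and mycophenolate and sirolimus are partly excepted. What remains is mainly rescue by other agents, in non-responders and in relapsers whom CsA and eltrombopag did not rescue. The protocol reports 5-year survival of 86% with early hematologic recovery against 40% without (2.9), and says that non-responders and less robust responders are more likely to progress to clonal disease (2.3.3).

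Censoring these subjects when rescue starts would be informative. Kaplan-Meier survival would be too high and clonal evolution too low, both in favor of the regimen. Clonal evolution matters more here: 9.2 gives it a historical benchmark and 9.5 leaves it out of the stopping rules, so long-term follow-up is where a signal would have to appear.

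**Working it through.** **1. Does 9.6 take these subjects off study?**

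| Place | Event on the 9.6 list | Stated consequence |
|---|---|---|
| 4.2.2 | Clonal disorder found late in a subject with very severe neutropenia | Off study, with a reference to 9.6 |
| 5.8 | Refractory h-ATG infusion reaction | Off study, with a reference to the off-study criteria |
| 9.6 | Pregnancy while not on drug | Exempted from withdrawal, so some listed events otherwise mean withdrawal |
| 5.6.1 | Thrombosis or embolism | Eltrombopag stops, CsA continues |
| 9.6 | Other immunosuppression | Study drug stops; off-study status not stated |

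The list mixes the two consequences. With the section title and the short follow-up rule, off study is the better reading for added immunosuppression, but the text does not settle it.

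**2. Illustrative size for 5-year survival.** The plan has no figure of its own to reproduce.

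Inputs:
- Survival at 5 years of 0.86 and 0.40 (2.9), by early recovery. These are applied here to responders and non-responders (assumption).
- Constant hazards (assumption): −ln(0.86)/5 = 0.0302 per year and −ln(0.40)/5 = 0.1833 per year.
- Non-response q: 2/13 = 15% (11 of 13 responded, 2.9.1), and 25% or 33% (Precis).
- Share f of surviving non-responders who start other immunosuppression: not in the documents; assumed 25%, 50% or 100%.
- Time of leaving t: month 6, or month 12 as an alternative (assumption).

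With full follow-up, S(5) = (1−q)·0.86 + q·0.40, which is 78.9%, 74.5% and 70.7% for the three values of q.

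With leavers censored at t, let A = (1−q)·exp(−0.0302t) and B = q·exp(−0.1833t). Then

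KM(5) = (A + B) · [(1−q)·0.86 + q(1−f)·0.40] / [A + (1−f)·B].

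Example with q = 1/3, f = 1, t = 0.5: A = 0.6567 and B = 0.3041, so KM(5) = 0.9608 × 0.5733/0.6567 = 0.839. Against 0.707 this is 13.2 points too high.

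| Non-response | Full follow-up | Bias, leaving at month 6 (f = 25% / 50% / 100%) | Bias, leaving at month 12 (same f) |
|---|---|---|---|
| 15% | 78.9% | +1.4 / +2.8 / +6.1 points | +1.2 / +2.4 / +5.2 points |
| 25% | 74.5% | +2.0 / +4.3 / +9.9 points | +1.7 / +3.7 / +8.4 points |
| 33% | 70.7% | +2.5 / +5.4 / +13.2 points | +2.1 / +4.6 / +11.3 points |

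**3. Scale against sampling error.** Section 9.2 analyzes cohorts separately, so the half-width 1.96·√[S(1−S)/n] is taken per cohort, at S = 0.789 and S = 0.707:
- n = 31: 14.4 and 16.0 points.
- n = 87: 8.6 and 9.6 points.

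The bias lies within the half-width for a 31-subject cohort throughout. In the extension cohort it reaches or passes the half-width only when nearly all non-responders leave and non-response is 25% or more.

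**4. Clonal evolution.** The documents give no evolution rates by response status, so only the direction can be stated: too low.

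**The case against.** The best counter-argument is that 9.6 stops study drug and nothing more. Its lead-in says just that, the limit at alternative therapy attaches most naturally to laboratory safety monitoring, and 6.4 and 9.4 require follow-up to 5 years without excluding anyone. Off study is never stated for this item. This stands as a possible reading. It does not remove the conflict, because the section is titled as off-study criteria, two other listed events lead off study, and nothing says that these subjects remain in follow-up.

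Several stronger readings are tempting but unsupported:

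- **The exceptions prove that the item means off study.** A reader might argue that no drug is scheduled after month 24, since CsA is "administered orally at a fixed dose through the 24 month timepoint", so an exception beyond 2 years could only concern study status. But 5.7 lets relapsers restart drug and remain on it until the end of the 5-year follow-up. The exceptions also make sense as stop-drug rules.
- **Survival will look better than a historical survival rate.** Section 9.2 gives no such rate, and 9.4 names only response and toxicity comparisons. The historical benchmark that is affected is clonal evolution.
- **Historical patients were followed through a second course while trial subjects leave at theirs.** The 9.2 wording describes who was treated. It does not say whether follow-up after a repeat course counted in the historical rates. An asymmetry is possible but not shown.
- **The bias should be judged against a pooled sample of all cohorts.** Section 9.2 treats each cohort separately, and the extension is descriptive (9.1).

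Further limits also stand. Transplant, the example of alternative therapy in 9.3, is not on the 9.6 list. Off-study subjects may enter protocol 94-H-0010, so loss of data is not automatic. Effective rescue therapy would shrink the bias.

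**Conclusion.** The point holds as an unresolved conflict between 9.6 and the 60-month follow-up in 9.4 and 6.4, with a known direction of bias if these subjects are taken off study and censored. It does not hold as a statement that the plan expressly ends their follow-up.

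The size, about 1 to 13 points too high on 5-year survival, is illustrative. It rests on assumed leaving shares of 25-100%, constant hazards, and early recovery standing in for response; the top of the range needs every surviving non-responder to leave. For clonal evolution no size can be given.

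The primary endpoint is untouched: 9.3 counts drop-outs and subjects who fail to respond and opt for alternative therapy before the 6-month evaluation as non-responders. The change should be made, because it removes a one-sided bias in long-term secondary endpoints at small cost.

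**What to change.** **Section 9.6.** Label each listed event as off protocol treatment or off study. State that starting other immunosuppression ends protocol treatment only, and that vital status and available cytogenetics are then collected yearly to month 60, through the home physician or protocol 94-H-0010.

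**Section 9.2.** State that survival and clonal evolution are analyzed regardless of later therapy, with death as a competing risk for evolution. Add a sensitivity analysis censored at the start of alternative therapy. Report by cohort how many subjects left at that point.

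**Subjects already off study.** Recover vital status, and cytogenetics where available, as far as consent allows.

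**Cost.** A few sentences in 9.6 and 9.2 and modest retrieval work. Some of the missing follow-up may not be recoverable.
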